**5.3 SUBJECT WITHDRAWAL OR TERMINATION**

**5.3.1 REASONS FOR WITHDRAWAL OR TERMINATION**

- A subject will be withdrawn from the study for the following medical or administrative reasons:
- Occurrence of an AE that represents an unacceptable risk to the subject and when continued participation in the investigational study is not warranted, in the judgment of the investigator, sponsor or medical monitor. The investigator must follow the subject until the AE resolves or is stable
  - Treatment with a prohibited concomitant medication other than the use of appropriate medications for the treatment of AEs under direction of the investigator
  - Subject noncompliance, defined as refusal or inability to adhere to the trial schedule or procedures
  - At the request of the subject or the subject’s legally authorized representative (e.g., subject withdraws consent), investigator, sponsor or regulatory authority
  - Pregnancy

**5.3.2 HANDLING OF PARTICPANT WITHDRAWALS OR TERMINATION**

Approximately 30 subjects will be enrolled in the study. Subjects will be encouraged to complete the study and all assessments. However, subjects may voluntarily withdraw at any time, and the investigator may discontinue individual subjects from the study at any time. For subjects who withdraw consent from the study, no study procedures will be done thereafter. For those that withdraw from receiving the study agent, follow-up visits and the safety phone follow-up, are to occur per the protocol. Excluding cases of medical emergency but prior to the discontinuation of a subject from the clinical study for disease worsening, the study investigator should discuss each case of discontinuation with the sponsor and/or the medical monitor.

- The subject withdrawal criterion below should be used to assess worsening or disease progression. In such cases, a documented assessment by the principal investigator is required, and subjects with clinically significant disease progression should be considered for withdrawal from the study and subsequent initiation of standard of care:
- A BCVA loss of  $\geq 5$  letters from baseline
  - New macular subretinal hemorrhage
  - Investigator discretion based on acute worsening of underlying disease or substantial risk to further participation in the study

**5.4 PREMATURE TERMINATION OR SUSPENSION OF STUDY**

Both the sponsor and the investigator reserve the right to terminate the study at any time. Should this be necessary, both parties will arrange discontinuation procedures and notify the appropriate regulatory authority(ies), IRBs, and IECs. In terminating the study, the sponsor and the investigator will continue to protect the subjects’ privacy and identity as required by relevant statues and regulations.

- Alkahest, Inc. has the right to terminate a study site from participating in the study at any time. Reasons for study or site termination may include, but are not limited to:
- Unsatisfactory subject enrollment (i.e., < 2 subjects enrolled within a 6-month period)
  - Unacceptable protocol deviations/violations as assessed by the medical monitor
  - Inaccurate or incomplete data entry and recording

- Investigational site non-compliance with ICH/GCP
- Unacceptable emergent safety profile

**6 TREATMENTS**

**6.1 STUDY AGENT DESCRIPTION**

**6.1.1 ACQUISITION**

The study agent will be formulated, tableted, labeled, packaged, and distributed by Alkahest, Inc.

**6.1.2 FORMULATION, APPEARANCE, PACKAGING, AND LABELING**

[REDACTED]

The subjects will be provided with 1 bottle at each treatment visit so that the time windows between visits (see [Section 15.1, Schedule of Events Table](#)) will be covered. The study agent will be delivered to the sites immediately prior to site activation and thereafter upon request. The product will be labeled for investigational use according to the relevant regulatory requirements for clinical studies.

For further details and information on ALK4290, including packaging and labeling, see the [REDACTED].

**6.1.3 PRODUCT STORAGE AND STABILITY**

[REDACTED] A temperature log must be maintained to make certain the study agent is stored at the correct temperature. If the storage conditions are found to be outside the specified range, the site must immediately notify the sponsor or designee.

**6.1.4 DOSING AND ADMINISTRATION**

The study agent will be self-administered orally twice daily for a total daily dose of 800 mg. Training on study agent administration will be conducted prior to initial study agent administration (at Visit 2) under the supervision of study personnel. All study agent administrations at the study site will be done under the direct supervision of the study personnel for documentation of precise administration times.

**6.2 STUDY AGENT ACCOUNTABILITY**

The investigator and/or pharmacist will receive the study agent delivered by the sponsor when the following requirements are fulfilled:

- Approval of the study protocol and Informed Consent by the IRB or IEC
- Availability of a signed and dated clinical trial contract between the sponsor and the investigational site
- Approval/notification of the appropriate regulatory authority

- Availability of the curriculum vitae of the principal investigator
- Availability of a signed and dated clinical trial protocol or immediately imminent signing of the clinical trial protocol

The investigator and/or pharmacist must maintain records of the study agent’s delivery to the trial site, the inventory at the site, the use by each subject, and the return to the sponsor or alternative disposition of unused study agent.

These records will include dates, quantities, batch/serial numbers, expiry (‘use by’) dates, and the unique code numbers assigned to the study agent and trial subjects. The investigator/pharmacist will maintain records that document adequately that the subjects were provided the doses specified by the protocol and reconcile all study agent received from the sponsor. At the time of final study agent reconciliation, the investigator/pharmacist must verify that all unused or partially used portion of study agent have been returned by the clinical trial subject and that no remaining study agent is retained by the investigator.

Accountability records must be maintained and readily available for inspection by representatives of Alkahest, Inc. or their designee and are open to inspection by regulatory authorities at any time. The accounts of any study agent accidentally wasted or intentionally disposed of must be maintained.

The disposal of used, partially used, or wasted study agent materials must be performed in accordance with the institution’s drug disposal policy. At study initiation, the clinical study monitor will evaluate the site’s standard operating procedure for study drug disposal/destruction to ensure it complies with study requirements. At the end of the study, following final study agent reconciliation by the monitor, the study site will be instructed by the sponsor to return or destroy all unused study agent supplies, including empty containers. A copy of the institution’s drug disposal policy should be maintained or referenced in the ISF.

**6.3 CONCOMITANT MEDICATIONS AND TREATMENTS**

All prescription, over-the-counter, and non-prescription medications (including herbal therapies and supplements) must be documented in the source documents and electronic Case Report Forms (eCRFs). All subjects should be maintained on the same medications at the same dosage and administration throughout the entire study period, as medically feasible, with no introduction of new chronic therapies. Any changes in medications should be documented in the eCRF with reason for change (e.g., adverse event, etc.).

**6.4 PROHIBITED TREATMENTS, MEDICATIONS, AND PROCEDURES**

[figure not shown]
[REDACTED]

No other interventional therapy for wAMD is concomitantly allowed.

The use of oral corticosteroids or high potency topical steroids (e.g. with systemic exposure) are restricted during the screening and treatment period of the study. The use of inhaled corticosteroids will be allowed if stably treated for 4 weeks prior to screening without a dose adjustment and not anticipated to require a dose adjustment during the study treatment period. The use of low potency topical corticosteroids (other than those intended for ocular application) will be allowed.

Primarily, no changes in concomitant therapy will be allowed except for treatments permitted according to [Section 6.3](#) above. However, in case of adverse events in need of treatment, symptomatic therapy according to the judgement of

the investigator will be permitted. All concomitant therapies and/or rescue therapies will be recorded on the appropriate pages of the eCRF.

**7 VARIABLES AND THEIR ASSESSMENT**

For the following endpoints, baseline is the value from Visit 2 (if not measured at Visit 2, then is the value from Visit 1). Detailed information on the methodology used with the following will be included in a Statistical Analytical Plan (SAP).

**7.1 THERAPEUTIC EFFECT**

BCVA will be assessed using ETDRS charts at 4 meters initial testing distance. The trained technicians measuring the BCVA using ETDRS should be the same throughout the study period. A detailed manual for performing refractions and measuring BCVA using the ETDRS testing method will be provided to investigators.

**7.2 SAFETY AND EXPLORATORY OUTCOMES**

Safety will be assessed by the incidence, seriousness, and severity of adverse events (AEs) (see [Section 7.2.1](#)). Changes in laboratory test results, vital signs, ECG, physical examination, and/or ocular morphologic investigations will be recorded as AEs/serious adverse events (SAEs) in the eCRF if they are judged clinically relevant by the investigator.

**7.2.1 ASSESSMENT OF ADVERSE EVENTS**

**7.2.1.1 Terminology to Use for Adverse Event Descriptions**

When reporting an adverse event, the event description should use the best matching terminology describing the event as found in the Common Terminology Criteria for Adverse Events (CTCAE v4.03). If an available CTCAE term fits the event well, no additional descriptors may be needed. However, necessary descriptions should be added in order to clarify the event or to place it in an appropriate context. The adverse event name should ideally be 1-3 words in length with additional description provided elsewhere on the adverse event report. A copy of the CTCAE is provided in the ISF. Standardized terms from the CTCAE will be used by the sponsor and the Contract Research Organization (CRO) to categorize events for reporting to regulatory authorities using the Medical Dictionary for Regulatory Activities (MedDRA, v. 20.1). In most cases, the CTCAE terms match MedDRA coding terminology. If an appropriate term matching the adverse event cannot be found in the CTCAE and the preferred MedDRA term is unknown, the AE description should include a diagnosis, sign, or symptom with additional information to facilitate subsequent categorization into MedDRA coding terms.

## 7.2.1.2 Definition of Adverse Events

### 7.2.1.2.1 Adverse Event

An AE is defined in the ICH E2D as “any unfavorable or unintended sign, symptom, or disease temporarily associated with the use of a medicinal product whether or not considered related to the product.” Progression or worsening of the medical condition under study, by itself, does not necessarily constitute an adverse event unless the change can be reasonably attributed to an action of the study agent and not only to its lack of efficacy. Simply defining an adverse event does not imply a causal relationship; relatedness to the study agent is defined in [Section 7.2.1.2.4](#).

### 7.2.1.2.2 Serious Adverse Event

An SAE is defined for this protocol as any AE that meets one or more of the following criteria:

- A. A death (CTCAE Grade 5 event) occurring during the study, whether or not considered treatment-related;
- B. A life-threatening event (CTCAE Grade 4);
- C. An event requiring inpatient hospitalization or prolonged hospitalization due to the adverse event;
- D. An adverse event resulting in a significant, persistent, or permanent change, impairment, damage or disruption in the participant’s body function or structure, physical activities or quality of life;
- E. An event that otherwise required a medical or surgical intervention to preclude permanent impairment or damage (excluding unrelated elective or cosmetic procedures).

### 7.2.1.2.3 Grading Severity of Adverse Events

The investigator must grade the severity of all reported adverse events into one of the following five (5) categories:

- Grade 1 (Mild)
- Grade 2 (Moderate)
- Grade 3 (Severe)
- Grade 4 (Life-Threatening)
- Grade 5 (Death)

The standardized CTCAE severity grading scales for the specific type of adverse event reported must be used when a matching CTCAE term is available. The highest severity grade experienced for the event should be reported. The initial severity grading may be updated in follow-up reports if the maximum grade changes to a higher level. The CTCAE grading scale should be used according the following guidelines.

#### ***Grade 1 (Mild)***

Transient (< 48 hours) or mild discomforts, no or minimal medical therapy or intervention required, hospitalization not necessary, no or little limitation in normal activities, nonprescription or single-use prescription therapy may be employed to relieve symptoms (e.g., aspirin for simple headache, acetaminophen with codeine for post-surgical pain). Mild adverse events may be listed as expected consequences of the therapy for any given protocol, and standard supportive measures for such an expected event do not necessarily elevate the event to a higher grade.

***Grade 2 (Moderate)***

Mild to moderate limitation in activity, some assistance may be needed; possibly none but usually minimal intervention/therapy required, hospitalization possible.

***Grade 3 (Severe)***

Marked limitation in activity, some assistance usually required; medical intervention/therapy required; hospitalization possible or likely.

***Grade 4 (Life-Threatening)***

Extreme limitation in activity, significant and immediate assistance required; significant medical/therapy intervention required to prevent loss of life; hospitalization, emergency treatment or hospice care probable. This grade is used when the subject was, in the view of the investigator, at substantial risk of dying at the time of the adverse event or it was suspected that use or continued use of the study agent would have resulted in the subject's death.

***Grade 5 (Death)***

Death related to AE.

**7.2.1.2.4 Relatedness of Study Agent to Adverse Event**

The investigator (or an authorized study physician) or sponsor must submit an attribution for the relatedness of the reported AE to the study agent. The attribution should take into account both the temporal association and any known physical, physiological, or toxicological information regarding the study agent that could reasonably infer causality. The three attribution categories are:

- **Definite** - Clearly related to the study agent. An adverse event that follows a temporal sequence from administration of the study agent; follows a known response pattern to study agent; and, when appropriate to the protocol, is confirmed by improvement after stopping the study agent (positive rechallenge; and by reappearance of the reaction after repeat exposure (positive rechallenge)); and cannot be reasonably explained by known characteristics of the subject's clinical state or by other therapies.
- **Possibly** - May be related to the study agent. An adverse event that follows a reasonable temporal sequence from administration of study agent and follows a known response pattern to the study agent, but could have been produced by the subject' clinical state or by other therapies.
- **Unrelated** - Clearly NOT related to the study agent. An adverse event that does not follow a reasonable temporal sequence after administration of the study agent and most likely is explained by the subject's clinical disease state or by other therapies. In addition, a negative rechallenge to the study agent would support an unrelated relationship.

**7.2.1.2.5 Worsening of Underlying Disease and/or Other Pre-Existing Conditions**

Worsening of the underlying disease and/or of other pre-existing conditions will be recorded as an AE/SAE in the eCRF.

### 7.2.1.2.6 Changes in Safety Evaluations

Changes in vital signs, ECG, physical examination, laboratory test results, and ophthalmic evaluations will be recorded as an AE/SAE in the eCRF if they are judged clinically relevant by the investigator.

### 7.2.1.2.7 Adverse Events of Special Interest

The following are considered adverse events of special interest (AESI):

- Hepatic injury defined by the following alterations of liver parameters:  
For subjects with normal liver function at baseline an elevation of AST and/or ALT  $\geq$  3-fold ULN combined with an elevation of total bilirubin  $\geq$  2-fold upper limit of normal (ULN) measured in the same blood draw sample. Subjects showing these lab abnormalities need to be followed up according to [Section 17.1.2](#).
- Abrupt decrease ( $>$  15 letters lost from baseline) of BCVA
- QTc prolongation ( $>$  +50 ms from baseline and  $>$  450 ms)

Protocol-specific AESIs are to be reported in an expedited manner similar to SAEs even if they do not meet any of the criteria for an SAE (see [Section 7.2.1.2.2](#)).

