### 5.2 EXCLUSION CRITERIA

**A subject will not be eligible for inclusion if any of the following criteria apply:**

- Treatment with IVT anti-VEGF therapy within 30 days preceding screening visit (Visit 1) in the study eye and/or planned concomitant IVT anti-VEGF treatment in the fellow eye during the study period
- Previous participation in any studies of investigational drugs within 1 month preceding screening visit (Visit 1)
- Any form of macular degeneration that is not age-related (e.g., Best's disease, Stargardt's disease, Sorsby's disease, etc.)
- Additional eye disease in the study eye that could compromise BCVA (i.e., uncontrolled glaucoma (intra-ocular pressure  $>$  24) with visual field loss, clinically significant diabetic maculopathy, history of ischemic optic neuropathy or retinal vascular occlusion, vitreomacular traction, monocular vision, or genetic disorders such as retinitis pigmentosa; high myopia  $>$  8 diopters)
- Anterior segment and vitreous abnormalities in the study eye that would preclude adequate observation with fundus photography/FA or SD-OCT

- Intraocular surgery in the study eye within 3 months prior to screening
- Aphakia or total absence of the posterior capsule (yttrium aluminum garnet (YAG) laser capsulotomy permitted, a minimum of 1 month prior to enrollment) in the study eye
- Known allergy to fluorescein sodium for injection in FA
- Current or planned use of medications known to be toxic to the retina, lens, or optic nerve (e.g. desferoximine, chloroquine/hydrochloroquine, chlorpromazine, phenothiazines, tamoxifen, nicotinic acid, and ethambutol)
- Medical history or condition:
  - Uncontrolled diabetes mellitus, with hemoglobin A1c (HbA1c) > 8%
  - Myocardial infarction or stroke within 12 months of screening
  - Active bleeding disorder
  - Concomitant use of warfarin or anticoagulation therapy
  - Major surgery within 1 month of screening or planned within the study period
  - Hepatic impairment
  - Uncontrolled hypertension
  - Positive screening for Hepatitis B, Hepatitis C, or Human Immunodeficiency Virus (HIV)
- 
- Use of systemic steroids (>10 mg prednisone or equivalent/day) within 14 days of first dose of study agent or known diseases which could require the use of systemic steroids within the study period
- Use of intravitreal steroids:
  - Dexamethasone (Ozurdex) or triamcinolone within 6 months prior to screening
  - Flucinolol (Retisert or Iluvien) within 48 months prior to screening

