- Patients with a clinically relevant abnormal screening hematology, blood chemistry, or urinalysis, if the abnormality defines a significant disease as defined in other exclusion criteria (e.g., aspartate aminotransferase (AST) or alanine aminotransferase (ALT) greater than 2.0-fold the upper limit of normal at screening; total bilirubin or prothrombin time (INR) > 1.5 times the upper limit of normal at screening). Laboratory testing may be repeated once during the screening phase
- Patients with impaired renal function defined as calculated glomerular filtration rate (GFR) < 30 mL/min
- Significant alcohol or drug abuse within past 2 years
- Based on electrocardiogram (ECG) reading, patients with a risk of prolonged QT interval effects including:
  - A marked baseline prolongation of QTc (using Bazett's formula:  $\geq 430$  ms in men and  $\geq 450$  ms in women) with confirmation on a repeat ECG)
  - A history of additional risk factors for Torsade de Pointes (TdP) (e.g., heart failure, hypokalemia, family, history of Long QT Syndrome, etc.)
  - The use of concomitant medications known to prolong the QT/QTc interval
- Significant disease or other medical conditions (as determined by medical history, examination, and clinical investigations at screening) that may, in the opinion of the investigator, result in the any of the following:
  - Put the patient at risk because of participation in the study
  - Influence the results of the study
  - Cause concern regarding the patient's ability to participate in the study
- Patients with malignancy for which the patient has undergone resection, radiation or chemotherapy within past 5 years; patients with treated basal cell carcinoma or fully cured squamous cell carcinoma are allowed

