### 7.2.1.3 Adverse Event and Serious Adverse Event Reporting

All AEs, serious and non-serious, occurring during the course of the clinical trial (i.e., from signing the informed consent through the follow-up period) will be collected, documented, and reported to the sponsor by the investigator on the appropriate eCRF and SAE reporting forms.

For each AE, the investigator will provide the onset date, end date, seriousness, grade, relatedness, treatment required, outcome, and action taken with the study agent. The investigator will determine the grade as defined in [Section 7.2.1.2.3](#) and the causal relationship to the study agent (relatedness) as defined in [Section 7.2.1.2.4](#).

The investigator must report the following events immediately (within 24 hours or the next business day whichever is shorter) to the sponsor or designee (refer to the Lab Manual/ISF for specific instructions): SAEs and non-serious AEs relevant to the reported SAE and protocol-specified AESI.

The investigator does not need to actively monitor subjects for adverse events once the clinical trial has ended. However, if the investigator becomes aware of an SAE(s) that occurred after the subject has completed the clinical trial, it should be reported by the investigator to the sponsor if considered relevant by the investigator.

Any AE occurring during the study must be documented in the subject's medical records and as an AE in the eCRF. Any SAE occurring during the study must be documented in the subject's medical records and as an SAE in the eCRF.

A separate SAE report should be used for each SAE. However, if at the time of initial reporting, multiple SAEs are present that are temporally and/or clinically related, they may be reported on the same SAE report.

The investigator should attempt to establish a diagnosis of the event (that meets the definition of an AE or SAE) based on signs, symptoms, and/or other clinical information. In such cases, the diagnosis should be

documented as the AE and/or SAE and not the individual signs or symptoms. The diagnosis will become the basis for the verbatim term as reported by the investigator. If no diagnosis is known and clinical signs and symptoms are not present, the abnormal finding should be recorded.

The investigator will take all appropriate and necessary therapeutic measures required for resolution of the AE. Any medication necessary for the treatment of an AE must be recorded on the concomitant medication case report form.

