**7.2.2 SAFETY LABORATORY EVALUATIONS**

Blood samples and urine must be collected at every visit. Safety laboratory examinations will include hematology, biochemistry, coagulation and qualitative urine analysis.

- Hematology: hemoglobin, red blood cell count (RBC), white blood cell count (WBC) with differential, platelets
- Biochemistry: glucose, sodium, potassium, calcium, inorganic phosphate, creatinine, aspartate aminotransferase (AST), alanine aminotransferase (ALT), alkaline phosphatase (AP), lactate dehydrogenase (LDH), total bilirubin (if elevated provide direct bilirubin), urea, total protein, albumin, uric acid
- Coagulation: activated partial thromboplastin time (aPTT), prothrombin time (PT)/international normalized ratio (INR)
- Urine: potential of hydrogen (pH), glucose, erythrocytes, leukocytes, protein, nitrite

Glomerular filtration rate (GFR) will be estimated by the Cockcroft Gault Formula utilizing serum creatinine (see [Section 17.5](#)). All safety laboratory measurements will be performed by a central laboratory. Investigators will get guidance and instructions on laboratory sampling and processing through a separate Lab Manual provided by the central laboratory.

The investigator is responsible for determining and documenting if out of range laboratory values are clinically significant or not. All clinically significant values will be recorded as AEs in the eCRF and followed until resolution. Once resolved, the appropriate eCRF page(s) will be updated.

---

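### The hepatic AESI is limited to subjects with normal baseline liver function, so eligible subjects with mildly raised values have no visible hepatic trigger for expedited reporting

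*Protocol*

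**What the plan says.** **The definition.** Protocol 7.2.1.2.7 begins the hepatic AESI with "For subjects with normal liver function at baseline an elevation of AST and/or ALT". It then requires AST and/or ALT at or above 3 × ULN together with total bilirubin at or above 2 × ULN in the same blood sample. SAP 16.1 repeats this with the same limitation. In the visible text, neither document attaches limits to the word normal or gives a criterion for subjects outside the clause. The other two AESIs, loss of visual acuity and QTc prolongation, are not limited to subjects with a normal baseline.

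**What AESI status does.** AESIs are expedited "even if they do not meet any of the criteria for an SAE". Protocol 7.2.1.3 sets a deadline of 24 hours or the next business day, whichever is sooner, for "SAEs and non-serious AEs relevant to the reported SAE and protocol-specified AESI". SAP 24 lists Table 14.3.5 for AESIs in the Safety set.

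**Who can be enrolled.** Protocol 5.2 excludes "Hepatic impairment" without a grade or laboratory limit. It also excludes AST or ALT "greater than 2.0-fold the upper limit of normal at screening", and "total bilirubin or prothrombin time (INR) > 1.5 times the upper limit of normal at screening". These limits are offered as examples of an abnormality that amounts to significant disease under the other exclusion criteria.

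**When baseline is taken.** Protocol 7 states: "For the following endpoints, baseline is the value from Visit 2", with Visit 1 as the fallback. SAP 9.2 uses the last measure before treatment.

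**Other capture.** Protocol 7.2.2 says of laboratory results: "All clinically significant values will be recorded as AEs in the eCRF and followed until resolution". Protocol 7.2.1.2.5 has worsening of pre-existing conditions recorded as an AE or SAE.

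**The concern.** The protocol chose to expedite one laboratory pattern, raised transaminases with raised bilirubin in the same sample, even when it is not serious. It then ties that trigger to a normal baseline, while its own screening limits sit above the upper limit of normal. Subjects between the ULN and those limits may be enrolled and treated, but on the plain meaning of the clause they have no hepatic trigger.

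For a non-serious case, AESI status is the visible route to the 24-hour report and to Table 14.3.5. The stake is therefore how fast the sponsor hears of such a case and whether the AESI table counts it. Whether the case is recorded at all is not in question.

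**Working it through.** The plan states no figure on this point, so there is nothing to reproduce. The check sets the definition beside the entry limits.

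**Inputs**

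| Item | Value | Source |
|---|---|---|
| AESI threshold, AST/ALT | ≥ 3 × ULN | Protocol 7.2.1.2.7, SAP 16.1 |
| AESI threshold, total bilirubin, same sample | ≥ 2 × ULN | same |
| Entry limit, AST/ALT | excluded above 2.0 × ULN | Protocol 5.2 |
| Entry limit, total bilirubin | excluded above 1.5 × ULN | Protocol 5.2 |
| Planned subjects | 30 | Protocol 10.5 |
| Post-dose laboratory visits | Visits 3 to 10 | Protocol 15.1 |

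**Step 1: the uncovered band.** AST/ALT above 1.0 and up to 2.0 × ULN, or bilirubin above 1.0 and up to 1.5 × ULN, is not excluded by the numeric limits and is not plainly normal.

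**Step 2: the rise needed to reach the thresholds** (threshold divided by baseline).

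- AST/ALT: 3.0/1.0 = 3-fold from the ULN; 3.0/2.0 = 1.5-fold from the entry limit.
- Bilirubin: 2.0/1.0 = 2-fold from the ULN; 2.0/1.5 = 1.33-fold from the entry limit.

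The 1.5-fold and 1.33-fold figures are the extreme case, with both values at the limit.

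**Step 3: a hypothetical subject.** Baseline ALT is 1.8 × ULN. A later sample shows ALT 3.5 × ULN and bilirubin 2.2 × ULN. Both thresholds are met (3.5 ≥ 3; 2.2 ≥ 2), and no SAE criterion is.

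| Meaning of normal | AESI? | 24-hour report and Table 14.3.5 |
|---|---|---|
| Values within the ULN (plain reading) | No | Not required |
| Passed the liver screen | Yes | Required |

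**Step 4: size.** If 30 subjects are treated, each case left out changes Table 14.3.5 by 1/30 = 3.3 percentage points. The documents give no share of subjects with raised baselines, so the expected number of cases cannot be calculated.

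**Step 5: does deleting the clause cause harm?** Both thresholds lie above the entry limits (3 against 2.0; 2 against 1.5), so a subject sitting at the limits does not qualify without a further rise. If every enrolled subject already counts as normal, deletion changes nothing. If not, it closes the gap.

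**Step 6: data needed for the count.** Visits 3 to 10 give 8 scheduled post-dose samples per subject; 8 × 30 = 240 at most for 30 subjects, all already planned.

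**The case against.** The best counter-argument is that the clause excludes no one. Protocol 5.2 presents its numeric limits as examples of disease under the other exclusion criteria, and the matching criterion is hepatic impairment. On that view, anyone who passed screening is hepatically normal. The link has weight and makes this a fair reading. It is not stated, though, and it leaves the clause with no function. It also gives no reason to keep the clause, since deletion would then change nothing.

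A second objection is that the case would reach the sponsor anyway. This largely stands. Clinically significant values are recorded and followed, worsening of a pre-existing condition is recorded, serious cases are expedited, one central laboratory runs the tests, and biochemistry shift tables and listings are planned. None of these puts a non-serious case on the 24-hour clock or in the AESI table.

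Third, part of Protocol 17.1.2 is redacted, and the SAP also refers to a clarification memorandum that is not among the two documents. A definition could sit in either. The point is therefore confined to the visible text.

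A reader might infer more than the documents support:

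- **That sites will report differently.** The wording permits this, but nothing shows that it would happen.
- **That liver events would be lost from the safety data.** The provisions above contradict this.
- **That these subjects would miss the liver work-up.** This cannot be judged with Section 17.1.2 partly redacted, and no claim is made.
- **That baseline itself is undefined.** The time point is fixed; only the word normal is open.

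**Conclusion.** The point holds as a minor one. On the plain reading, eligible subjects with mildly raised baseline liver values fall outside the hepatic AESI, and the visible text offers them no alternative criterion. The consequence is limited to the speed of reporting and the count in Table 14.3.5 for a non-serious case.

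For the gap to matter, several things must coincide among about 30 subjects treated for 6 weeks: a raised baseline, both thresholds met in one sample, no SAE criterion met, and the narrow meaning of normal applied. The number affected is unknown and may be zero. The primary analysis of visual acuity is unaffected. The conclusion assumes that no unseen text defines the term or adds a branch for other subjects.

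**What to change.** In Protocol 7.2.1.2.7 and SAP 16.1, delete the opening clause that restricts the hepatic AESI to subjects with a normal baseline, so that the existing thresholds apply to all treated subjects. In the SAP, add a count, taken from the central-laboratory data, of Safety-set subjects who meet both thresholds in the same post-dose sample, and show baseline liver status in the listing.

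If the sponsor's safety physicians want to keep a baseline condition, they should define it by analyte, limit and visit, and state the criterion for everyone else.

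The cost is a protocol amendment, which Protocol 12.2 requires to have IRB/IEC approval before it is implemented, and one extra table line. No new samples are needed. There may be a few extra expedited reports, because a smaller rise reaches the thresholds from a raised baseline. Those reports would concern a pattern that the protocol already chose to expedite.
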